4.2.2. Extension Safety Population

The Extension Safety population is defined as all enrolled patients who received any amount of open-label study drug in study MVT-601-3003. All safety analyses will be performed using the Extension Safety population, unless otherwise specified. Safety data will be analyzed by parent study treatment group according to the actual treatment received (not the randomized treatment). Any patient who received at least one dose of relugolix will be considered as a relugolix patient, consistent with analysis in the parent study.

4.3. Definitions, Computation, and Convention

4.3.1. Definition of Date of First Dose and Date of Last Dose of Parent Study Drug

The date of first dose of parent study drug is defined as the date when a patient receives the first dose of study drug (relugolix/placebo or E2/NETA/placebo) following randomization in study MVT-601-3001 or MVT-601-3002. The date of last dose of parent study drug is defined as the date a patient receives the last dose of study drug in the parent study, prior to or on the Week 24

visit date. The exact date of last dose of parent study drug will be known for all patients entering the MVT-601-3003 study.

4.3.2. Definition of Date of First Dose and Date of Last Dose of Extension Study Drug

The date of first dose of extension study drug is defined as the date when a patient receives the first dose of open-label study drug (relugolix or E2/NETA) in the MVT-601-3003 study. The date of last dose of extension study drug is defined as the date a patient receives the last dose of open-label study drug in the MVT-601-3003 study. If the complete date of last dose of extension study drug is unknown, the last date the extension study drug was dispensed will be used. For patients missing only day for date of last dose of extension study drug, either first of the month of last dose of extension drug or last date extension study drug was dispensed will be used, whichever is later.

4.3.3. Study Day

Study day will be calculated with respect to the date of the first dose of study drug in the parent study (Study Day 1). For assessments conducted on or after the date of the first dose of parent study drug, study day will be calculated as:

$$(\text{Assessment date} - \text{date of first dose of parent study drug}) + 1$$

For assessments conducted before the date (and time) of the first dose of parent study drug, study day will be calculated as:

$$(\text{Assessment date} - \text{date of first dose of parent study drug})$$

4.3.4. Extension Study Day

Extension study day will be calculated with respect to the date of the first dose of open-label study drug in the extension study (Extension Study Day 1). For assessments conducted on or after the date of the first dose of extension study drug, extension study day will be calculated as:

$$(\text{Assessment date} - \text{date of first dose of extension study drug}) + 1$$

For assessments conducted before the date (and time) of the first dose of extension study drug, extension study day will be calculated as:

$$(\text{Assessment date} - \text{date of first dose of extension study drug})$$

For patients who do not receive any amount of extension study drug, extension study day will be calculated as above with respect to the date of enrollment in the extension study.

4.3.5. Definition of Treatment Duration

Overall treatment duration is defined as the duration of time from the date of the first dose of parent study drug to the date of the last dose of extension study drug as follows:

$$(\text{Date of last dose of extension study drug} - \text{Date of first dose of parent study drug}) + 1$$

For patients missing day and month for date of last dose of extension study drug, the last date extension study drug was dispensed will be used to calculate treatment duration. For patients missing only day for date of last dose of extension study drug, the later of first of the month of

last dose of extension drug or last date extension study drug was dispensed will be used to calculate treatment duration.

4.3.6. Definition of Extension Study Treatment Duration

Treatment duration in the extension study is defined as the duration of time from the date of the first dose of extension study drug to the date of the last dose of extension study drug as follows:

$$(\text{Date of last dose of extension study drug} - \text{Date of first dose of extension study drug}) + 1$$

For patients missing day and month for date of last dose of extension study drug, the last date extension study drug was dispensed will be used to calculate treatment duration. For patients missing only day for date of last dose of extension study drug, the later of first of the month of last dose of extension drug or last date extension study drug was dispensed will be used to calculate treatment duration.

4.3.7. Definition of Baseline Value and Post-Baseline Value

Unless otherwise specified, Baseline values are defined as the last measurement before the first administration (date and time) of study drug in the parent study. A post-Baseline value is defined as a measurement taken after the first administration of study drug. Change from Baseline is defined as (post-Baseline value – Baseline value). Both date and time of study drug administration and measurement will be considered when calculating Baseline value. If the time is not available, then the date alone will be used. For patients who receive no study medication, the date of randomization will be used in place of the date of first dose in determining Baseline and post-Baseline values.

4.3.8. Visit Windows

Visit windows, which will be used to associate assessments with a scheduled visit, will be used only for summarizing data by visit. The windows for scheduled assessments are shown in [Table 2](#), [Table 3](#) (BMD), [Table 4](#) (electrocardiogram [ECG]), [Table 6](#) (UFS-QoL), and [Table 6](#) (transvaginal ultrasound and EQ-5D-5L) respectively. For safety assessments, the study day will be used to determine the associated visit window. There will be no separation of data from the parent and extension study. For example, if an assessment in the extension study falls in the Week 24 visit window, it will be summarized as Week 24.

If the results from more than one assessment are within a given visit window, the non-missing result from the assessment closest to the target date will be used. If two assessments are equally close to the target day, the earlier assessment will be used. For summaries of shift from Baseline in safety parameters, all values will be considered for these analyses.

Table 2: Visit Windows for Monthly Assessments

Visit	Start Day	Target Day	End Day
Week 4 ^a	1	29	43
Week 8	44	57	71
Week 12	72	85	99
Week 16	100	113	127
Week 20	128	141	155
Week 24	156	169	183
Week 28	184	197	211
Week 32	212	225	239
Week 36	240	253	267
Week 40	268	281	295
Week 44	296	309	323
Week 48	324	337	351
Week 52	352	365	Date of last dose + 6 ^b
Safety Follow-Up ^c	Date of last dose + 7 days	Date of last dose + 30 days	Date of last dose + 60 days

^a Start day of Week 4 for study day 1 includes only post-Baseline assessments that occurred after the first dose.

^b End day of Week 52 is date of last dose + 1 for patients entering the MVT-601-035 study.

^c The safety follow-up visit window will be restricted to assessments prior to the date of initiation of another investigational agent or hormonal therapy affecting the hypothalamic-pituitary-gonadal axis or surgical intervention for uterine fibroids.

Table 3: Visit Windows for Bone Mineral Density Assessments

Visit	Start Day	Target Day	End Day
Week 12	64	85	106
Week 24	148	169	196
Week 36	197	253	308
Week 52	309	365	421

Assessments will be excluded from analysis if they occur on or after the date of initiation of another investigational agent or hormonal therapy affecting the hypothalamic-pituitary-gonadal axis or surgical intervention for uterine fibroids. Assessments after date of last dose of extension study drug + 30 days will also be excluded from analysis.

Table 4: Visit Windows for Week 12, 24, and 52 Assessments (ECG)

Visit	Start Day	Target Day	End Day
Week 12	64	85	106
Week 24	148	169	196
Week 52	309	365	421

Table 5: Visit Windows for Week 12, 24, 36, and 52 Assessments (UFS-QoL)

Visit	Start Day	Target Day	End Day
Week 12	64	85	106
Week 24	148	169	196
Week 36	197	253	308
Week 52	309	365	421
Safety Follow-up ^a	Date of last dose + 7 days	Date of last dose + 30 days	Date of last dose + 60 days

^a The safety follow-up visit window will be restricted to assessments prior to the date of initiation of another investigational agent or hormonal therapy affecting the hypothalamic-pituitary-gonadal axis or surgical intervention for uterine fibroids.

Table 6: Visit Windows for Week 24 and 52 Assessments (Transvaginal Ultrasound, EQ-5D-5L, Endometrial Biopsies)

Visit	Start Day	Target Day	End Day
Week 24	128	169	196
Week 52	309	365	421
Safety Follow-up ^a	Date of last dose + 7 days	Date of last dose + 30 days	Date of last dose + 60 days

^a The safety follow-up visit window will be restricted to assessments prior to the date of initiation of another investigational agent or hormonal therapy affecting the hypothalamic-pituitary-gonadal axis or surgical intervention for uterine fibroids.

Table 7: Time Window for Feminine Product Collection

Visit	Feminine Product Collection Visit Date ^{a,b}	Time Window ^a
Week 28	X_1	(Date of Extension Study Day 1) - < X_1
Week 32	X_2	$(X_1 + 1) - \leq X_2$
Week 36	X_3	$(X_2 + 1) - \leq X_3$
Week 40	X_4	$(X_3 + 1) - \leq X_4$
Week 44	X_5	$(X_4 + 1) - \leq X_5$
Week 48	X_6	$(X_5 + 1) - \leq X_6$
Week 52/EOT	X_{Last}^c	(Previous Feminine Product Returned Visit + 1)] – $\leq X_{Last}$

^a If feminine products are collected at more than 1 visit within a given visit window (Table 2), the last feminine product collection date will be used to define the time window. If the patient missed the previous visit, a planned study visit date will be used to calculate the window.

^b In the absence of feminine product collection due to amenorrhea the visit date when amenorrhea was reported will be used.

^c Date of last non-missing feminine product collection within the interval from (last dose date – 35) to (last dose date + 7 days) (see Section 7.2.2).

General Rules for Missing Data

Handling of missing data for the primary efficacy analysis is described in Section 7.2.4.

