2.2. Sample Size Considerations

Because this is an extension study, the sample size will be determined by the numbers of patients who have completed either parent study (MVT-601-3001 or MVT-601-3002) and who are eligible and willing to participate in this study. No formal statistical testing has been planned.

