7.1.2. Analyses for Continuous Data

Continuous variables will be summarized using descriptive statistics (eg, n, mean, median, SD, minimum, and maximum). For the analyses of change from Baseline, the mean at Baseline will be calculated for all patients with at least one post-Baseline value by treatment group. Additionally, the mean will also be calculated for each visit, including only the patients who are in the analysis who have data for that visit by treatment group.

For endpoints evaluating the change (absolute or percent change) from Baseline to Week 52, mean change as well as least squares (LS) means change and 95% CI will be summarized. LS means and 95% CI will be derived separately for each treatment group using a mixed model repeated measures approach with randomization stratification factors included as fixed effects. The Baseline value will be included as a covariate, and an unstructured variance-covariance matrix will be assumed. If the mixed model fails to converge, a first-order autoregressive variance-covariance matrix will be used. Calculation of the dependent variable (change from Baseline) for each patient at each visit will be calculated based on the visit windows specified in [Section 4.3.8](#). In addition, summary statistics (mean change or mean % change) will be graphically presented as appropriate.

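### SAP Table 2 leaves off-drug follow-up laboratory and vital-sign results from early discontinuers eligible for the Week 28 to Week 48 summaries, because only the Week 52 window is cut at last dose

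*SAP*

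**What the plan says.** SAP Section 4.3.8 sets the visit windows used for by-visit summaries. Its assignment rule is: "For safety assessments, the study day will be used to determine the associated visit window". In Table 2 the extension rows run from "Week 28 184 197 211" to "Week 48 324 337 351" (start, target and end day). None of these rows refers to the last dose.

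Week 52 starts on Day 352 and ends 6 days after last dose. A footnote shortens this for one group: "End day of Week 52 is date of last dose + 1 for patients entering the MVT-601-035 study". The Safety Follow-Up row opens at "Date of last dose + 7 days", has its target at + 30 days and closes at "Date of last dose + 60 days".

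Where several results fall in one window, the one closest to target is used. Nothing covers one result that fits two windows.

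SAP 7.3.3 sends hemoglobin change to the methods of 7.1.2, where a mixed model is fitted: "Calculation of the dependent variable (change from Baseline) for each patient at each visit will be calculated based on the visit windows specified in" (the cross-reference is to 4.3.8). SAP 9.2 and 9.3.2 present laboratory and vital-sign changes at each post-baseline visit.

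**The concern.** Protocol Section 6.2 describes the visits at Weeks 28 to 52 as on-treatment. A woman who stops early still has a Follow-up visit about 30 days after her last dose (Protocol 4.5 and 6.3). The Schedule of Activities marks vital signs and clinical laboratory tests, which include a complete blood count, at that visit.

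The study day of her Follow-up visit usually lies inside one of the Week 28 to 48 windows. Under the study-day rule her off-drug values can be tabulated as on-treatment values, or appear in two rows. Two programmers could follow the SAP faithfully and produce different tables.

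Values drifting back toward baseline off drug would blur the on-treatment picture. For hemoglobin, bleeding that resumes after stopping could lower the value, which would count against the drug rather than for it.

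**Working it through.** **Inputs.** Day limits come from SAP Table 2. The Follow-up visit is at about last dose + 30, with a window of -3 to +18 days (Protocol Table 1), so last dose + 27 to + 48. The last dose is taken at the Early Termination visit (Protocol Table 1, dosing footnote). The Week 24/Baseline visit may fall from Day 159 (169 - 10), so no last extension dose is earlier than that. Let L be the study day of the last dose.

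**Reproducing the grid.** With target = 7 × week + 1, end = target + 14 and start = previous end + 1, Week 28 is 184/197/211, Week 48 is 324/337/351 and Week 52 starts on Day 352. All twelve fixed rows of Table 2 match.

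**Overlap of windows.** Safety Follow-Up is [L + 7, L + 60] and the Week 28 to 48 block is [184, 351]. They meet when L + 7 ≤ 351 and L + 60 ≥ 184, that is, for every L from 159 to 344. Week 24 (ending Day 183) also overlaps when L ≤ 176. A scheduled follow-up cannot land there, however, since its earliest day is 159 + 27 = 186. Only an unscheduled or early result could.

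**Where the follow-up result lands.** At L + 30 it is inside Weeks 28 to 48 for L = 159 to 321 (321 + 30 = 351). At L + 27 the limit is L = 324, and at L + 48 it is L = 303.

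| Last dose | Safety Follow-Up window | Result at + 30 | Also falls in |
|---|---|---|---|
| 200 | 207 to 260 | 230 | Week 32 (212 to 239) |
| 225 | 232 to 285 | 255 | Week 36 (240 to 267) |
| 250 | 257 to 310 | 280 | Week 40 (268 to 295) |
| 309 | 316 to 369 | 339 | Week 48 (324 to 351) |
| 321 | 328 to 381 | 351 | Week 48 (324 to 351) |
| 365 | 372 to 425 | 395 | none |

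**Does the closest-to-target rule remove it?** No. Windows are 28 days wide, so results on L and L + 30 never share one. At L + 27 they share a window only when L is its first day. The Early Termination result then wins (13 days from target against 14).

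**Other limits.** Table 2 footnote c (new hormonal therapy, another investigational agent or fibroid surgery) restricts only the Safety Follow-Up row. The exclusion after last dose + 30 sits under Table 3 and covers BMD only.

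**Size, by assumption.** Take 600 women, 5% to 25% stopping early, last doses spread evenly over Days 170 to 351 (182 days), and all attending follow-up at + 30. Days 170 to 321 (152 days) place the result in Weeks 28 to 48, and 152/182 = 0.835. Then 600 × 0.05 × 0.835 = 25 and 600 × 0.25 × 0.835 = 125 records. Over six windows that averages about 4 to 21 per window.

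**The case against.** The strongest reply is that Table 2 has a row made for this visit, anchored to last dose with its target at + 30, and that a sensible programmer would use it. That is a natural reading, so the exact statement is that the off-drug results are eligible for the on-treatment rows and not excluded from them. It does not remove the defect: the only written rule is study day, and it points to the on-treatment row.

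It is also true that the analysis is descriptive ("No formal statistical testing has been planned") and that the main results are out of reach. The primary endpoint uses the Table 7 collection interval, bounded at last dose + 7. BMD has its own cut-off. ECG is not scheduled at follow-up. Shift tables use worst post-baseline values whatever the window. The protocol's treatment-emergent period itself extends to about 30 days after last dose, although that does not make an off-drug value a Week 40 on-treatment value.

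Three stronger readings are tempting and not supported:

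- A reader might infer that Tables 5 and 6 carry the same fault, since their Week 52 rows run to Day 421. For a last dose on Day 365, Days 372 to 421 (50 of the 54 follow-up days) lie in both windows. But UFS-QoL, ultrasound, EQ-5D-5L and biopsy are not scheduled at the Follow-up visit, so there is almost nothing to misassign. This is wording cleanup at most.
- A reader might infer that off-drug hemoglobin enters the Week 52 estimate. The Week 52 window ends at last dose + 6, so no Safety Follow-Up value enters it. Any effect on the Week 52 LS mean is indirect, through the repeated-measures model. The Week 52 hemoglobin proportions are untouched.
- A reader might apply the 25 to 125 records to the hemoglobin model. SAP 7.3.3 restricts that analysis to women with baseline hemoglobin of 10.5 g/dL or less, so its share is smaller, and the documents do not allow it to be counted.

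**Conclusion.** The point holds in a limited form. The overlap follows from Table 2 by arithmetic, no precedence rule resolves it, and the closest-to-target rule does not help at + 30 days. It exposes the by-visit laboratory and vital-sign summaries at Weeks 28 to 48 and, for a subset, the hemoglobin model at the same visits. Women who complete to Day 365 are not affected.

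The number of records is unknown because no discontinuation rate is given. The range of roughly 25 to 125 rests on the assumed 5% to 25% early stopping, evenly spread last doses and full attendance at follow-up. The consequence is ambiguity and some dilution in descriptive tables, with no threat to the primary or bone conclusions. It should be settled before database lock because the remedy is already half-written in the SAP.

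**What to change.** Add one rule under Table 2. Each post-baseline window ends at the earlier of its listed end day and last dose + 6, keeping the existing + 1 limit at Week 52 for women entering MVT-601-035. Results from last dose + 7 onward go to Safety Follow-Up only, subject to that row's own limits. State that last dose means the last dose of extension study drug, since SAP 4.3.1 and 4.3.2 define one for each study. Every on-treatment window then closes by L + 6 and Safety Follow-Up opens at L + 7, so no overlap can remain for any L.

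The cost is one sentence and one programming condition, with slightly fewer records at Weeks 28 to 48. There is one real downside. Where the last-dose date is unknown, SAP 4.3.2 substitutes the last dispensing date, which may precede the true last dose, so some on-treatment results could move to follow-up. Flag those cases and review them. An Early Termination visit held more than 6 days after the last dose would move in the same way and should be flagged too.

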1.1. Schedule of Activities

Table 1: Schedule of Activities for Study MVT-601-3003

PERIOD	OPEN-LABEL TREATMENT									SAFETY FOLLOW-UP
	VISIT NAME (Timing is relative to MVT-601-3001/-3002)	Week 24/Baseline (Week 24 of Parent Study; Baseline of Extension Study)	Week 28	Week 32	Week 36	Week 40	Week 44	Week 48	Week 52 ^a (or Early Termination of Study Drug)	
Visit Window (days)	Parent Study Day 169 - 10 to + 20	± 7	± 7	± 7	± 7	± 7	± 7	± 10	-	- 3 to + 18
Informed Consent	X ^d									
Review Eligibility Criteria	X									
Concomitant Medications ^e	X ^f	X	X	X	X	X	X	X	X	X
Vital Signs (BP, HR, Temperature)	X ^g	X	X	X	X	X	X	X	X ^h	X
Weight	X ^g			X				X	X ^h	
Complete Physical Examination	X ^g							X		
Visual Acuity ⁱ	X ^g									
Signs and Symptoms-Directed Physical Examination ⁱ		X	X	X	X	X	X		X ^h	X
12-Lead ECG ^k	X ^g							X	X ^h	
Clinical Laboratory Tests ^l	X ^{g,m}	X	X	X	X	X	X	X ^m	X ^h	X
Pharmacodynamics Sample ⁿ	X ^{g,m}							X ^m	X ^{h,m}	
Urinalysis	X ^g							X	X ^h	
Pregnancy Test (Urine)	X ^g	X	X	X	X	X	X	X	X ^h	X

PERIOD	OPEN-LABEL TREATMENT									SAFETY FOLLOW-UP
VISIT NAME (Timing is relative to MVT-601-3001/-3002)	Week 24/Baseline (Week 24 of Parent Study; Baseline of Extension Study)	Week 28	Week 32	Week 36	Week 40	Week 44	Week 48	Week 52 ^a (or Early Termination of Study Drug)	Un-scheduled ^b	Follow-Up ^c (~30 days after last dose of study drug)
Visit Window (days)	Parent Study Day 169 - 10 to + 20	± 7	± 7	± 7	± 7	± 7	± 7	± 10	-	- 3 to + 18
Transvaginal Ultrasound ^o	X ^g							X ^p	X ^h	
Bone Densitometry ^d	X ^g			X				X ^{p,r}	X ^h	
Endometrial Biopsy	X ^{g,s}							X ^p	X ^h	
Dispense Study Treatment	X	X	X	X	X	X	X		X ^h	
Patient Paper Diary ^t	X	X	X	X	X	X	X	X	X	
Dispense Feminine Products	X	X	X	X	X	X	X		X ^h	
Feminine Product Collection and Venous Blood Sample ^u	X ^g	X	X	X	X	X	X	X	X ^h	
Treatment Compliance		X	X	X	X	X	X	X	X ^h	
Take Study Drug Dose in Clinic ^v	X ^w							X	X ^h	
Daily Self-Administration of Study Treatment ^v		X								
MIQ ^x	X ^g	X	X	X	X	X	X	X	X ^h	X
UFS-QoL Questionnaire ^x	X ^g			X				X	X ^h	
EQ-5D-5L Questionnaire ^x	X ^g							X	X ^h	
Adverse Event Collection ^y	X ^z	X	X	X	X	X	X	X	X	X
Status of Menstruation Recovery										X ^{aa}

BP, blood pressure; ECG, electrocardiogram; EQ-5D-5L, European Quality of Life Five-Dimension Five-Level Scale; HR, heart rate; MIQ, Menorrhagia Impact Questionnaire; UFS-QoL, Uterine Fibroid Symptom and Health-Related Quality of Life

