- ^a The week 52 visit must occur on or after the 1-year anniversary of Study Day 1 in the parent study. The timing of the visit should also be at least 28 weeks (± 10 days) from the actual date of the Week 24/Baseline visit.
- ^b Unscheduled visits may be conducted at the investigator's discretion when needed. The reason for the visit will be captured in the source documents.
- ^c The Follow-up visit may be waived if the patient enrolls directly into another relugolix clinical study upon completion of the Week 52 visit.
- ^d May be signed up to 30 days prior to the Week 24/Baseline visit or during the Week 24/Baseline visit. Enrollment in MVT-601-3003 is defined by administration of the first dose of MVT-601-3003 study drug.
- ^e Record all prescription and nonprescription drug and supplements taken from the Week 24/Baseline visit through the Safety Follow-Up period. Concomitant medications with start date prior to the first dose of study drug for MVT-601-3003 should be reported as concomitant medications in the parent study (MVT-601-3001 or MVT-601-3002). Concomitant medications initiated during the MVT-601-3001 or MVT-601-3002 studies and ongoing at the time of the first dose in Study MVT-601-3003 will be recorded in the electronic case report form.
- ^f Concomitant medications are recorded both for the parent study and for MVT-601-3003 at the Week 24/Baseline visit. (See footnote c for further details).
- ^g This is a parent study (MVT-601-3001 or MVT-601-3002) Week 24 procedure that serves as the Week 24/Baseline procedure for MVT-601-3003 and is covered under the informed consent for the parent study.
- ^h The indicated procedure may be performed at the Unscheduled visit based on the purpose of the visit (eg, follow-up for an adverse event or abnormal laboratory test).
- ⁱ See parent study protocols (MVT-601-3001 or MVT-601-3002) for instructions on testing visual acuity.
- ^j The exam may include a gynecologic examination, if indicated based on signs and symptoms.
- ^k The 12-lead ECGs will be submitted for central reading.
- ^l Clinical laboratory tests at each visit include clinical chemistries and a complete blood count. At the Week 24/Baseline visit and Week 52 visit, additional tests include: fasting (at least 8 hours) glucose, lipid profile, and hemoglobin A1c.
- ^m Samples should be obtained in a fasted state (at least 8 hours). Water is allowed during the fasting period.

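### SAP Table 2 ends the Week 24 window at Day 183 while the protocol allows that visit to Day 189, so late in-protocol Week 24 assessments are labelled Week 28

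*SAP*

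**What the plan says.** Protocol Section 1.1 (Schedule of Activities, Table 1) gives the window for the Week 24/Baseline visit as "Parent Study Day 169 - 10 to + 20", that is, Days 159 to 189. Weeks 28 to 48 have ±7 days and Week 52 has ±10 days. The heading of the visit row says timing is relative to the parent studies. Footnote a requires Week 52 to fall on or after the one-year anniversary of parent Study Day 1, and at least 28 weeks (±10 days) "from the actual date of the Week 24/Baseline visit".

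SAP Section 4.3.8 assigns assessments to visits on parent study day and does not restart the count at extension entry: "For example, if an assessment in the extension study falls in the Week 24 visit window, it will be summarized as Week 24". The Table 2 rows that matter (start, target, end) are "Week 24 156 169 183", "Week 28 184 197 211" and "Week 48 324 337 351". Week 52 opens on Day 352 with target Day 365 and closes 6 days after the last dose (1 day after, for women entering MVT-601-035). When several results share a window, "the non-missing result from the assessment closest to the target date will be used", and ties go to the earlier one. Tables 3 to 6 in the same section end Week 24 at Day 196.

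SAP Section 7.1.2 computes change from Baseline for the repeated-measures models from these windows.

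**The concern.** A woman can have her Week 24 assessments on a day that the protocol permits and, before she has taken any extension drug, have them reported under an extension visit. Tables 3 to 6 leave room for the permitted range and Table 2 does not, which suggests an oversight rather than a choice.

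Two things are at stake. The first is the Week 24 summary itself, which loses these women. The second depends on scheduling. If the monthly extension visits run from the actual entry date, the late start carries through to the end of the study. Every label is then one visit too high, a Group C woman's last value on placebo appears as Week 28, and her Week 48 value competes with her Week 52 value for the same window. Hemoglobin at Week 52 is a secondary endpoint and a blood count is taken at every visit, so a competing value would exist.

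**Working it through.** **Reproducing Table 2.** Target = 7 × week + 1. End day = midpoint of adjacent targets, so Week 24 ends at (169 + 197)/2 = 183. This rule returns all 12 closed windows in Table 2 and the Week 52 start of Day 352.

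**The mismatch.** Latest permitted Week 24/Baseline day = 169 + 20 = 189. Days 184 to 189 are permitted but lie in the Week 28 window: 6 of 31 days.

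**Reading A: Weeks 28-48 run every 28 days from entry day w.** Then Week 48 = w + 168 and Week 52 = w + 196.

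- Week 48 enters the Week 52 window when w + 168 ≥ 352, so w ≥ 184.
- It is nearer to Day 365 than Week 52 is when |w − 197| < |w − 169|, so w > 183.

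| Entry day | Label of entry visit | Week 48 day (distance to 365) | Week 52 day (distance) | Reported as Week 52 |
|---|---|---|---|---|
| 183 | Week 24 | 351 (14; own window) | 379 (14) | Week 52 |
| 184 | Week 28 | 352 (13) | 380 (15) | Week 48 |
| 186 | Week 28 | 354 (11) | 382 (17) | Week 48 |
| 189 | Week 28 | 357 (8) | 385 (20) | Week 48 |

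For entry on Days 184-189 with on-schedule visits, the visits at Weeks 24, 28, … 48 are labelled Weeks 28, 32, … 52.

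Now allow ±7 days at Week 48, ±10 days at Week 52, and Week 52 no earlier than Day 366. The earliest entry day at which Week 48 can displace Week 52 satisfies w + 168 + 7 ≥ 352, so w = 177. Weighting every permitted pair of visit days equally (an assumption, since actual visit timing is not in the documents):

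- Entry Day 177: 6/270 = 2%
- Entry Day 183: 105/315 = 33%
- Entry Day 184: 132/315 = 42%
- Entry Day 189: 267/315 = 85%
- Days 184-189 pooled: 1207/1890 = 64%

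**Reading B: Weeks 28-48 stay on parent study days.** The permitted days are 190-204, 218-232, 246-260, 274-288, 302-316 and 330-344. Each range lies inside its own Table 2 window. Week 48 is at latest Day 344 and cannot reach Day 352. The entry value is 8 to 13 days from target Day 197 and the real Week 28 visit at most 7, so the real visit is used. The loss is the Week 24 value only.

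**Testing the remedies under Reading A.**

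- Moving only the Week 24 end day to 189 corrects the entry label, but for entry on Days 184-189 the Week 28 to 48 visits are still labelled Weeks 32 to 52.
- Windowing post-entry visits on Extension Study Day (targets 29, 57, … 197, boundaries midway between them) labels every visit correctly, including all ±7 and ±10 day deviations.

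**Reach.** Tables 3 to 6 run Week 24 to Day 196. Where they include Week 52, it covers Days 309-421, so their endpoints are safe. The primary endpoint uses a collection interval tied to the last dose (SAP Table 7 and Section 7.2.2).

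**The case against.** The strongest objection is that the schedule heading places visits on the parent-study clock and footnote a ties only Week 52 to entry. On that reading nothing after Week 24 shifts, Group C's Week 28 value is a real on-treatment value, and the defect is a missing Week 24 value. This stands as far as it goes, and it is why the label shift and the displacement can only be stated conditionally. It does not settle the matter. For entry on Days 184-189 it would put nominal Week 28 only 8 to 13 days after entry, and leave 43 to 48 days between nominal Week 48 (Day 337) and Week 52 (Days 380-385). That sits poorly with monthly pregnancy tests (Protocol Section 4.6) and with product collection intervals of up to 35 days (SAP Section 7.2.2.3).

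Three further objections have force:

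- The Week 24/Baseline visit is dated by completion of its last procedure, while results are windowed on their own dates. A visit completed on Day 186 may include blood drawn by Day 183, which is labelled correctly.
- Day 357 is about 51 weeks from parent Baseline and Day 385 about 55, so taking the value nearest Day 365 is a defensible meaning of Week 52. Requiring the last on-treatment value instead would be partly a preference.
- Later values are not lost altogether. Shift summaries use all values, selected laboratory thresholds are also summarized on the last on-treatment observation (SAP Section 9.2), and listings show everything.

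None of these defends labelling a pre-extension-dose assessment as Week 28.

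**Conclusion.** The Table 2 mismatch is real and does not depend on how later visits are scheduled: assessments made before the first extension dose on Days 184-189 are in protocol and are mislabelled. The further effects rest on the assumption that Weeks 28-48 follow the entry date. Under it, displacement of Week 52 by Week 48 is certain for entry on Days 184-189 only with exact 28-day spacing. With the permitted windows it is possible from entry Day 177 but not certain.

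A reader might infer that Week 52 results are generally unreliable, or that every late entrant has Week 48 reported as Week 52. The documents support neither. The exposed data are by-visit summaries and repeated-measures models that use Table 2: hemoglobin, chemistry, vital signs and, for the labels, by-visit menstrual blood loss (for collections, a Table 7 footnote takes the last one in a window). The primary responder endpoint, bone mineral density and the other Table 3 to 6 endpoints, and the shift tables are not affected. Tests taken in the extension only at Week 52, such as estradiol, have no Week 48 competitor.

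The number of women entering on Days 184-189 is not in the documents. Purely as an assumption, 2% to 10% of 600 would be 12 to 60 women, and fewer in the hemoglobin change analysis, which is restricted to baseline values of 10.5 g/dL or less. The study is descriptive, so no test result depends on this.

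**What to change.** 1. In SAP Section 4.3.8, label any Table 2 assessment made before the first extension dose as Week 24, through Day 189.
2. State whether Weeks 28-48 are timed from parent Study Day 1 or from the actual Week 24/Baseline date, and reconcile the schedule heading with footnote a.
3. If the anchor is the entry date, window post-entry Table 2 assessments by nominal visit or on Extension Study Day, which Section 4.3.4 already provides: "Extension study day will be calculated with respect to the date of the first dose of open-label study drug in the extension study". A Week 48 assessment then cannot be summarized as Week 52. Extending the Week 24 end day alone would not achieve this.

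The cost is a change to one SAP table and its text, with the matching programming. No new data are needed.
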